8.3 Prohibited Therapy During Study Period

The following medications are prohibited for the duration of the study starting from acquisition of patient consent. However, any patients taking these medications after screening should not be withdrawn from the study unless there are safety concerns. If applicable, the possible effects of these medications on the primary endpoint will be considered.

- Any new medications or interventions for epilepsy (including ketogenic diet and VNS) or changes in dosage.
- Patients should not take any more than three AEDs inclusive of CLB.
- Recreational or medicinal cannabis or synthetic cannabinoid based medications (including Sativex) within three months prior to or during the study.

If any other IMP is taken as part of a clinical trial within twelve weeks of the screening visit or during the study, the patient must be withdrawn from this study.

8.4 Compliance in Investigational Medicinal Product Administration

Patients or their caregivers will record the total volume of IMP, administered on each treatment day, using the paper diary and will be asked to return all IMP (used and unused) at each subsequent visit. The site will check the returned IMP against the usage recorded in the diary and the projected usage. Any discrepancies will be discussed with the patient/caregiver and documented accordingly within the patient's source documents.

The investigator must inform GW promptly of all missing or unaccountable IMP.

Records of IMP accountability will be maintained according to [Section 5.3.4.](#)

8.5 Access to Blinded Treatment Assignment

The identity of IMP assigned to patients will be held by the IVRS. The principal investigator (PI) at each center is responsible for all trial-related medical decisions and is responsible for ensuring that information on how to access the IVRS is available to the relevant staff in case of an emergency and unblinding is required. A patient's treatment assignment must only be unblinded when knowledge of the treatment is essential to make a decision on the medical management of the patient. Unblinding for any other reason will be considered a protocol deviation.

The investigator is encouraged to contact GW to discuss the rationale for unblinding. However, to prevent delays to the investigator or medical personnel responding to a potentially emergent situation, unblinding of study medication will not be dependent upon the investigator receiving approval from GW (i.e., the investigator will be able to obtain the code break information independent of contacting GW).

If the investigator does unblind they must contact GW within one working day of the event and must document the time, date and reasons for unblinding in the patient's CRF.

9. STUDY PROCEDURES

A list of the required study procedures is provided in the subsections that follow, refer also to the Schedule of Assessments [APPENDIX 1](#). Assessments or tests that are not done and examinations that are not conducted must be reported as such on the CRFs.

The location of the source data for the following procedures will be documented, per center, in a signed ‘Source Data Verification plan’, for further details see [Section 16.2](#).

9.1 Study Procedure Listing

9.1.1 Contraception

To be eligible for the study, the patient must have agreed that if they or their partner are of child-bearing potential they are willing to use highly effective contraception for the duration of the study and for three months thereafter. A highly effective method of birth control is defined as those which result in a low failure rate (i.e., less than 1% per year) when used consistently and correctly such as combined or progesterone only oral contraceptives, intrauterine device, intrauterine hormone-releasing system, bilateral tubal occlusion, vasectomized partner or sexual abstinence⁶. Abstinence, as referenced above, is only acceptable as true abstinence: when this is in line with the preferred and usual lifestyle of the patient; periodic abstinence (e.g., calendar, ovulation, symptothermal, post-ovulation methods) and withdrawal are not acceptable methods of contraception. The use of hormonal contraception must be supplemented with a barrier method (preferably male condom).

9.1.2 Informed Consent

Adult patients with an adequate level of understanding must personally sign and date the IRB/EC approved informed consent form(s) before any study specific procedures are performed or any patient related data is recorded for the study. For adult patients with an insufficient level of understanding of what is proposed, only personal legal representative consent will be sought. The informed consent process should be documented within the patient notes.

GW requires a physician to be present for consent and to also sign the consent forms.

9.1.3 Demographics

Patient demographics will be recorded at Visit 1. The following information will be obtained for each patient: date of birth, gender and race (if allowed per local regulations).

9.1.4 Medical History

Relevant, significant medical history (including seizure information since diagnosis, history of epilepsy-specific genetic testing and all prior AEDs taken) will be obtained during Visit 1 and is defined as any condition or disease that:

- May affect the condition under study.
- Is ongoing on entry into the study.

9.1.5 Concomitant Medication

Details of all current and recent medication (i.e., taken within the previous 28 days) including AEDs will be recorded at the screening visit (Visit 1) and reviewed at each subsequent visit. AEDs used during the study should be maintained at a stable dose. Any changes in concomitant medication during the study must be recorded in the CRF at study visits. Patients should stop taking any prohibited therapy prior to the screening visit, as defined in [Section 8.3](#).

9.1.6 Physical Examination

A physical examination will be performed at the screening visit (Visit 1) to ensure that the patient is eligible to enter the study. To ensure patient safety, further physical examinations will be performed at every hospital visit. Physical examinations will include height (at screening) and body weight measurements.

9.1.7 Vital Signs

Vital sign measurements, taken after five minutes rest in a sitting position, will be completed alongside the physical examination at all visits. Postural BP will be assessed after five minutes in supine position and, if possible, two minutes in standing position. The pulse rate must also be measured as part of the vital sign assessments. BP and pulse rate must be recorded using the same arm throughout the study.

9.1.8 12-Lead Electrocardiogram

An ECG will be performed, after five minutes in supine position, at all hospital visits. A physician must review the ECG and any abnormal findings considered to indicate significant medical history or AEs must be recorded appropriately in the CRF. Additional ECG measurements can be taken at any time during the study, if clinically indicated.

9.1.9 Clinical Laboratory Sampling

Laboratory tests will be undertaken at all hospital visits and will include hematology, biochemistry, and urinalysis (provided urine can be obtained, with the exception of

screening where a urine sample for THC screen must be obtained). A serum alcohol test will be performed at Visits 1, 2 and 4. A serum pregnancy test (if appropriate) will also be performed at Visit 1.

Urine samples for biochemistry will be analyzed at the study center by use of a dipstick with any relevant findings being sent for further laboratory based urinalysis (urinalysis, microscopy, culture and sensitivity, as applicable).

The investigator and study monitor will be provided with a list of the normal ranges used by the testing laboratory for all variables assayed during the study and a statement of accreditation (or similar) for the laboratory. Clinical laboratory sample parameters are detailed in [Table 9.1.9-1](#).

Table 9.1.9-1 Hematology, Biochemistry, Urinalysis and THC Screen

Biochemistry (serum)	Hematology (whole blood)	Urinalysis (urine)	Pregnancy Test	THC screen (urine)
Alanine aminotransferase (ALT)	Hematocrit	Bilirubin	Serum	THC
Albumin	Hemoglobin	Blood		
Alkaline phosphatase	Mean cell volume	Glucose		
Aspartate aminotransferase (AST)	Mean corpuscular hemoglobin	Ketones		
Calcium	Platelets	Nitrites		
Creatinine	Red blood cell count	pH		
Estimates of glomerular filtration rate	White blood cell count with automated differential	Protein		
Gamma-glutamyl transferase		Specific gravity		
Glucose		Urobilinogen		
HDL-cholesterol				
Potassium				
Prolactin				
Prothrombin time (plasma)				
Sodium				
Total bilirubin (TBL)				
Total protein				
Urea (BUN)				
Triglycerides				

All laboratory results will be reviewed and the reports signed by an investigator. Any results considered to be of clinical significance must be addressed and followed up as clinically appropriate. See [Section 12.8](#) for guidance on evaluation of potential drug-induced liver injury. All laboratory results considered by the investigator to represent an AE must be documented on the CRF.

Repeat samples will be taken, if required, for clinical follow up or if the sample is lost or damaged. Any abnormal end of treatment clinical laboratory result of clinical significance must be repeated at regular intervals until it returns to normal, or until an

investigator is satisfied that the abnormality is not related to the IMP and needs no further investigation.

Sample volume requirements and processing procedures will be detailed in a separate laboratory manual. The patient/caregiver must be advised that it may not be safe for them to undertake further blood tests within one month of any study-related blood draws and to inform the investigator if they suffered any blood loss in the four weeks prior to screening.

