6.2 Exclusion Criteria

The patient may not enter the study if ANY of the following apply:

- 6.2.1 Patient has clinically significant unstable medical conditions other than epilepsy.
- 6.2.2 Patients on CLB at doses above 20 mg per day.
- 6.2.3 Patients taking CLB intermittently as rescue medication.
- 6.2.4 Patient has a history of symptoms (e.g., dizziness, light-headedness, blurred vision, palpitations, weakness, syncope) related to a drop in blood pressure (BP) due to postural changes.
- 6.2.5 Any history of suicidal behavior or any suicidal ideation of type four or five on the C-SSRS in the last month or at screening.
- 6.2.6 Patient has had clinically relevant symptoms or a clinically significant illness in the four weeks prior to screening or enrollment, other than epilepsy.
- 6.2.7 Patient has consumed alcohol during the seven days prior to enrollment and is unwilling to abstain during the blinded phase of the study.
- 6.2.8 Patient is currently using or has in the past used recreational or medicinal cannabis, or synthetic cannabinoid based medications (including Sativex[®]) within the three months prior to study entry.
- 6.2.9 Patient has any known or suspected history of any drug abuse or addiction.
- 6.2.10 Patient is unwilling to abstain from recreational or medicinal cannabis, or synthetic cannabinoid based medications (including Sativex) for the duration for the study.
- 6.2.11 Patient has consumed grapefruit or grapefruit juice seven days prior to enrollment and is unwilling to abstain from drinking grapefruit juice within seven days of PK visits.
- 6.2.12 Patient has any known or suspected hypersensitivity to cannabinoids or any of the excipients of the IMP, e.g., sesame oil.

6.2.13 Female patient is of child bearing potential, or male patient's partner is of child bearing potential; unless willing to ensure that they or their partner use highly effective contraception for the duration of the study and for three months thereafter. Highly effective methods of contraception are defined as those, alone or in combination, that result in a low failure rate (i.e., less than 1% per year) when used consistently and correctly. Such methods include hormonal contraceptives, intrauterine devices/hormone-releasing systems, bilateral tubal occlusion, vasectomized partner or sexual abstinence.

6.2.14 Female patient who is pregnant (positive pregnancy test), lactating or planning pregnancy during the course of the study and for three months thereafter.

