
6.2.15 Patients who have received an IMP within the 12 weeks prior to the screening visit.

6.2.16 Any other significant disease or disorder which, in the opinion of the investigator, may either put the patient at risk because of participation in the study, may influence the result of the study, or the patient's ability to participate in the study.

6.2.17 Following a physical examination, the patient has any abnormalities that, in the opinion of the investigator would prevent the patient from safe participation in the study.

6.2.18 Patient has significantly impaired hepatic function at screening (Visit 1) or enrollment (Visit 2), defined as any of the following:

- Alanine aminotransferase (ALT) or Aspartate aminotransferase (AST) $>5 \times$ upper limit of normal (ULN).
- ALT or AST $>3 \times$ ULN **and** total bilirubin (TBL) $>2 \times$ ULN **or** international normalized ratio (INR) >1.5 .
- ALT or AST $>3 \times$ ULN with the presence of fatigue, nausea, vomiting, right upper quadrant pain or tenderness, fever, rash, and/or eosinophilia ($>5\%$).

*This criterion can only be confirmed once the laboratory results are available; patients randomized into the study who are later found to meet this criterion **must** be withdrawn from the study.*

6.2.19 Unwilling to abstain from donation of blood during the study.

6.2.20 Travel outside the country of residence planned during the study.

6.2.21 Patients previously enrolled into this study.

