9.2.1 Double Blind Phase

9.2.1.1 Visit 1 (Day -14 to -7, Screening)

The following observations will be made at Visit 1: demographics, medical history (including seizure information since diagnosis, history of epilepsy-specific genetic testing and all prior AEDs taken), concomitant medications (including AEDs), physical examination (including height and body weight), ECG, vital signs and AEs.

Clinical laboratory samples (blood and urine) will be taken for hematology, biochemistry, alcohol testing, THC testing, urinalysis and a pregnancy test (using a serum sample, if appropriate). The laboratory results should be available within 3-5 working days after Visit 1. If the results show a patient is ineligible, the patient will not be enrolled into the study. The C-SSRS will be administered.

Patients who satisfy all inclusion and none of the exclusion criteria specified in [Section 6](#) will be assigned a unique patient number and then begin the baseline period. Patients or their caregivers will be given a paper diary to record daily seizure information, rescue medication, concomitant AEDs and AEs; and will be instructed on how to do so. The investigator must record the patient's attendance at the visit and confirm the outcome of screening on the CRF.

9.2.1.2 Visit 2

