9.2.1.2.1 Visit 2 (Day 1) – Enrollment (+3 days)

This visit will occur 7–14 days after Visit 1.

The following observations will be made at Visit 2: concomitant medications, (including AEDs), physical examination (including body weight), ECG, vital signs and review of patient diary and AEs.

Clinical laboratory samples (blood and urine) will be taken for hematology, biochemistry, alcohol testing and urinalysis. Blood samples will also be taken for genetic testing if additional consent has been obtained. The C-SSRS will be administered. The investigator must record the patient's attendance at the visit, and confirm the outcome of the visit prior to enrollment.

Following enrollment patients will begin the PK sampling process. Blood samples will be taken for analysis of plasma concentrations of CLB, N-CLB, CBD, CBD major metabolites, THC and THC major metabolites. A baseline PK sample will be taken before the patient takes their morning dose of CLB. Further samples will then be taken at the following times relative to the CLB dose: 15 minutes, 30 minutes, 1 hour, 1.5 hours, 2 hours, 4 hours, 6 hours and 12 hours. Patients will either remain in clinic overnight throughout this PK sampling process or return to the clinic on Day 2 ahead of additional sample collection.

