9.2.1.2.2 Visit 2 (Day 2) - Enrollment

This is the second part of the two day enrollment visit. The final PK sample will be collected 24 hours after the Day 1 morning CLB dose.

Following completion of the PK sampling process the following observations will be made on Day 2: concomitant medications (including AEDs), physical examination (including body weight), vital signs and AEs.

GWP42003-P/placebo will be dispensed and both the morning dose of CLB and of GWP42003-P/placebo will be taken in clinic. Patients and/or their caregivers will be provided with individual dosing schedules as described in [Section 8.1.2](#). Each patient will then receive their GWP42003-P/placebo for the 10 day titration period followed by the 21 day maintenance period. Patients, or their caregivers, will be instructed on how to record the diary information.

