10. WITHDRAWAL

In accordance with the Declaration of Helsinki³¹, the FDA regulations relating to good clinical practice (GCP) and clinical trials^{32,33,34}, the EU Clinical Trials Directive (2001/20/EC)³⁵ and/or other applicable regulations, a patient has the right to withdraw from the study at any time and for any reason without prejudice to his or her future medical care by the physician or at the institution.

The patient must be withdrawn from the study if any of the following apply:

- Administrative decision by the investigator, GW, or a Regulatory Authority.
- Pregnancy.
- Protocol deviation that is considered to potentially compromise the safety of the patient.
- Withdrawal of patient consent.
- Withdrawal of legal representative consent.
- Lost to follow up.
- ALT $>3 \times$ ULN or AST $>3 \times$ ULN **and** (TBL $>2 \times$ ULN **or** INR >1.5).
- ALT or AST $>3 \times$ ULN with the appearance of fatigue, nausea, vomiting, right upper quadrant pain or tenderness, fever, rash, and/or eosinophilia ($>5\%$).
- ALT or AST $>8 \times$ ULN.
- ALT or AST $>5 \times$ ULN for more than two weeks.
- Any other IMP is taken as part of a clinical trial during the study.

Patients may also be withdrawn from the study for any of the following:

- Patient non-compliance.
- AE, which in the opinion of the investigator, would compromise the continued safe participation of the patient in the study.
- Any evidence of drug abuse or diversion.
- Suicidal ideation or behavior of type four or five during the treatment period, as evaluated with the C-SSRS.

Should a patient request or decide to withdraw from the study, all efforts must be made to complete and report the observations as thoroughly as possible up to the date of withdrawal. Patients who withdraw should have their dose of IMP tapered gradually (10% each day) over a period of 10 days, beginning at the time the decision

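### The only scheduled pregnancy test is at Visit 1, 8 to 15 days before first dose; none is scheduled before first dose at Visit 2, before open-label dispensing, or during up to a year of open-label treatment

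*Protocol*

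**What the plan says.** In Protocol Version 2, exclusion 6.2.14 covers a "Female patient who is pregnant (positive pregnancy test", as well as women who are lactating or planning pregnancy. Section 10 opens its compulsory list with "The patient must be withdrawn from the study if any of the following apply", and pregnancy is on that list.

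Testing is set in Section 9.1.9: "A serum pregnancy test (if appropriate) will also be performed at Visit 1". The Visit 1 procedures (9.2.1.1) agree. The Version 2 blinded-phase schedule, reproduced in Appendix 1.4 of Amendment 1, has one mark for the pregnancy test, under Visit 1. The same schedule marks eligibility at both Visit 1 and Visit 2 Day 1. The Version 2 OLE schedule there has no pregnancy-test row.

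At Visit 2 Day 1 (9.2.1.2.1) the laboratory work is hematology, "biochemistry, alcohol testing and urinalysis", with optional genetic testing. The next day (9.2.1.2.2), "GWP42003-P/placebo will be dispensed and both the morning dose of CLB" and the first dose of study solution are taken in clinic. Visit 4 (9.2.1.4.1 and 9.2.1.4.2) and OLE Visits 5 to 12 (9.2.2.1 to 9.2.2.8) list no pregnancy test.

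Two other provisions bear on this. Sections 6.2.13 and 9.1.1 require highly effective contraception during the study and for three months afterwards. Section 12.4 requires a pregnancy to be reported within 24 hours of the site learning of it.

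**The concern.** An exclusion that turns on a test result is only as current as the test. Here the result can be two weeks old at first dose, and it is never refreshed. A woman who conceived shortly before Visit 1 and tested negative, or who conceived after it, passes the Visit 2 eligibility check because nothing at that check would show the pregnancy. The mandatory withdrawal then operates only once the pregnancy becomes apparent some other way, and the reporting rule in 12.4 starts from the same moment.

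What is at stake is exposure of a pregnancy to the study drug. Section 3.2 says there is very little human adverse-event information on cannabidiol, and 8.1.2 allows up to 30 mg/kg/day in the OLE. The matter is one of patient safety and visit scheduling. The protocol itself fixes it, and a statistical analysis plan could not supply it.

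**Working it through.** **Inputs**
- Visit 1 to Day 1: 7 to 14 days, with a +3-day window on Visit 2 (9.2.1.2.1).
- First dose of study solution: Day 2 (8.1, 9.2.1.2.2).
- OLE dispensing: Day 34 (9.2.1.4.2). OLE length: up to one year, taken as 365 days (4.1). End-of-taper visit: ten days after Visit 11 (9.2.2.8).
- End-of-taper visit without the OLE: Day 43 (9.2.1.5). Last dose: Day 42 (9.2.1.4.2) or Day 43 (8.1.2).
- Contraceptive failure: below 1% per year when used consistently and correctly (6.2.13).
- Women of child-bearing potential: not stated. A range of 5 to 12 of the 20 patients is assumed.

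**Time from the only test to first dose**
- Shortest: 7 + 1 = 8 days.
- Longest: 14 + 1 = 15 days, or 14 + 3 + 1 = 18 days if the window is added.

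**Time from the only test to the end of taper**
- Without the OLE: 7 + 42 = 49 days to 14 + 42 = 56 days.
- With a full OLE: 7 + 33 + 365 + 10 = 415 days to 14 + 33 + 365 + 10 = 422 days (425 with the Visit 2 window).

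**Expected pregnancies during dosing (illustration)**
- Without the OLE, dosing runs from Day 2 to Day 43, 42 days. 5 × 0.01 × 42/365 = 0.006; 12 × 0.01 × 42/365 = 0.014.
- With a full OLE, dosing runs to about Day 34 + 365 + 10 = Day 409, 408 days or 408/365 = 1.12 years. 5 × 0.01 × 1.12 = 0.06; 12 × 0.01 × 1.12 = 0.13.

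**Effect of the added tests**
- A Visit 2 Day 1 test cuts the interval before first dose from 8 to 15 days (18 with the window) to 1 day.
- At 3-month intervals in the OLE, the longest untested stretch is about 92 days, or 92 + 7 + 7 = 106 days if both ±7-day windows are used in full.
- A Visit 2 test only 7 days after Visit 1 may still miss a conception around screening. A Visit 4 test on Day 33, nominally 7 + 32 = 39 to 14 + 32 = 46 days after Visit 1, is the backstop. It limits such exposure to about 32 dosing days (Day 2 to Day 33).

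**Tests added**
- Per woman: 2 without the OLE (Visits 2 and 4), or 6 with a full OLE (plus Months 3, 6, 9 and 12).
- For 5 to 12 women: 10 to 24 tests if none enters the OLE, 30 to 72 if all complete it.

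**The case against.** The strongest reply is that the risk is already controlled. Section 7 counts patients as enrolled from consent, so the contraception requirement arguably covers the interval between Visit 1 and Day 2. Women planning pregnancy are excluded. Adverse events and concomitant medication are reviewed, and a physical examination is done, at every OLE clinic visit. On the assumptions above, the 15-day interval alone carries 5 to 12 × 0.01 × 15/365 = 0.002 to 0.005 expected pregnancies. All of this stands, and it limits the weight of the point. But none of these measures detects an early pregnancy, and the protocol still treats pregnancy as an exclusion, a compulsory withdrawal and a reportable event.

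It can also be said that no document gives a reproductive-risk figure from which to derive a testing interval in the OLE. That is correct, so the interval should be the sponsor's to choose.

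Some stronger readings are tempting but not supported:
- *The protocol contradicts itself.* It does not. The sections on testing agree with one another, and 6.2.14 sets no date for the test.
- *Pregnancy alone lacks a recheck that hepatic function receives.* Exclusion 6.2.18 does read "Patient has significantly impaired hepatic function at screening (Visit 1) or enrollment (Visit 2". However, the THC screen behind the cannabis exclusion is also done at Visit 1 only. And 6.2.18 allows the criterion to be confirmed after randomization, so it does not establish a check completed before dosing.
- *The caution in 9.1.9 about further blood tests rules out serum.* It concerns additional tests around study draws and does not bear on an assay run on a sample already scheduled.
- *The contraception rules conflict because 9.1.1 adds a barrier method that 6.2.13 does not mention.* Both are met by following 9.1.1, so this is a drafting matter.

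**Conclusion.** The point holds as a worthwhile safety improvement. One serum test at Visit 1 supports an exclusion applied up to 15 days later (18 with the window) and a withdrawal rule that runs for up to about 422 days after it in a patient who completes the OLE. As written, dosing can begin or continue through an undetected pregnancy.

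The case rests on making the protocol's own criteria workable at small cost, not on frequency. The illustrative count is about 0.01 without the OLE and about 0.1 with it. A reader might take these as upper bounds. They are not: the 1% rate assumes consistent and correct use, the number of women is assumed, and pregnancies missed by the Visit 1 test are not counted. Assuming that every woman completes a full OLE pulls the other way.

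The PK endpoints and their analysis are unaffected. The supplied text ends before Version 2's own Appendix 1, so the schedule evidence is the Version 2 table in Amendment 1, which agrees with Sections 9.1.9 and 9.2.

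**What to change.** In 9.1.9, the visit descriptions and the schedules, for women of child-bearing potential:
- Add an on-site urine pregnancy test at Visit 2 Day 1, with the result known before the Day 2 first dose. Use same-day serum if no urine can be obtained.
- Add another at Visit 4, before OLE dispensing.
- Repeat it periodically at existing OLE clinic visits, at an interval the sponsor chooses (for example every 3 months, at Months 3, 6, 9 and 12).
- Confirm any positive result in serum.

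Urine suits because of turnaround. For screening, "The laboratory results should be available within 3-5 working days after Visit 1"; a similar delay at Visit 2 would miss the next-day dose. On-site reading is already routine: "Urine samples for biochemistry will be analyzed at the study center by use of a dipstick". Amendment 1 also added repeat alcohol tests at Visits 2 and 4, so repeat testing at those visits is practicable.

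The cost is a protocol amendment, 2 urine tests per woman without the OLE or about 6 with a full OLE at 3-month intervals, and a possible delay to first dose while a false positive is resolved. No extra visit is needed.
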